14 DATA REPORTING / REGULATORY REQUIREMENTS

Adverse event lists, guidelines, and instructions for AE reporting can be found in Section 10 (Adverse Events: List and Reporting Requirements). The Data Safety Monitoring Plan is described in Section 14.3.

14.1 Data Collection

The Herbert Irving Comprehensive Cancer Center has an electronic clinical trials and data management system (CTMS) that will be used for data collection. CRFs for the study will be built into the CTMS for data entry. The system has full auditing capabilities which is web-based and housed on a server in a fully HIPAA compliant server room with restricted access and video camera monitoring. All users must login with their own application username and password. Users off campus must first access the Virtual Private Network with their assigned campus username and password and then use their application credentials. Users are only able to see study information if they are indicated as study personnel in our electronic IRB system. Users are limited to access based on the role assigned in their corresponding protocol. Subject data is

entered directly into the system, which (in the case of Columbia subjects) confirms the correct identity of subjects via an interface with the electronic medical subject index. Staff with the appropriate IRB defined roles can run reports within the system for reporting purposes.

14.2 Data Reporting

Case Report Forms will be completed for each subject enrolled into the clinical study through the CTMS. It is the investigator's responsibility for ensuring that all clinical and laboratory data entered on the corresponding CRFs are complete, accurate and authentic.

14.3 Data and Safety Monitoring Committee

The NCI-approved Data Safety and Monitoring Committee (DSMC) of the Herbert Irving Comprehensive Cancer Center (HICCC) will monitor every subject who receives treatment on this protocol for toxicity. This protocol will adhere to the policies of the currently approved HICCC Data and Safety Monitoring Plan (DSMP), which is in accordance with NCI and CUMC-IRB policy and guidelines. The committee is chair is appointed by the HICCC Director. The committee consists of HICCC faculty and staff with expertise in oncology, research pharmacy, research nursing, and data management. The DSMC convenes twice a month to review subject safety and the conduct of the trial. The PI will submit data and safety monitoring reports to the DSMC at a frequency to be determined by the DSMC based on risk to the subjects.

At the time of renewal, the study team will submit the most recent DSMC approval letter for safety review to the CUMC IRB. Any modifications that are required by the DSMC to ensure subject safety will be submitted to the IRB. All protocol deviations, violations, and eligibility waivers will be submitted to and approved by the DSMC prior to being reported to the IRB. All study data reviewed and discussed during these meetings will be kept confidential.

For multicenter research, the principal investigator will assure that there is a mechanism in place to distribute the report to all participating investigators for submission to their local IRB. The report will document that a review of data and outcomes across all centers took place on a given date. It will summarize the DSMC's review of the cumulative toxicities reported from all participating sites without specific disclosure by treatment arm. It will also inform site investigators of the study the DSMC's conclusion with respect to progress or need for modification of the protocol.

14.4 Quality Control and Quality Assurance

Independent monitoring of the clinical study for protocol and GCP compliance will be conducted periodically by the CPDM Compliance Core on behalf of the HICCC DSMC. Additionally, the Compliance Oversight Committee of the IRB at Columbia University Medical Center may audit the study at any time per institutional policies and procedures. The investigator-sponsor and Columbia University Medical Center will permit direct access of the study monitors and appropriate regulatory authorities to the study data and to the corresponding source data and documents to verify the accuracy of this data.

Columbia University Medical Center
Herbert Irving Comprehensive Cancer Center
Version Date: January 30, 2024

A risk-based approach will be used by the Compliance Core to determine the frequency, number of subject charts, and data elements to be monitored. The Compliance Coordinator will review the study status and summarize enrollment, toxicities, SAEs/UPs, dose escalation, statistical endpoints (e.g., stopping rules), etc. for the full DSMC membership at the regularly scheduled meetings.

Internal On-site Monitoring:

- Initial, recurrent, and close-out on-site monitoring visits will also be conducted at remote clinical sites, as appropriate/feasible. Other sites will have monitoring performed remotely (see below for further details).
- The study Monitoring Visit Log will be completed and signed by the monitor and the PI/CRNP/CRN and/or CRC and will be filed in the regulatory binder.
- The Compliance Coordinator will communicate with the site coordinator/Site Principle Investigator to schedule the monitoring visit and arrange for access to study materials and documentation.
- The assigned Compliance Coordinator will monitor this trial within 1 month after the first subject is enrolled and throughout the life of the study to ensure that the study is being conducted in accordance with the protocol, GCP, applicable federal and local regulations, and per all applicable SOPs. The Compliance Coordinator is responsible to notify the PI and CRNP/CRN/CRC of upcoming monitor visits and convey what information and documentation will be required for the visit(s). The Compliance Coordinator is responsible for verifying that informed consent is properly obtained, eligibility is met (via the central registration process), and all study procedures are conducted according to the study protocol. The Compliance Coordinator will also verify that the data reported in the CRF's accurately reflect source documents, that all toxicities have been reported to date, and that all SAE's/UPs/deviations/violations have been reported according to local IRB and HICCC DSMC requirements. The Compliance Coordinator will issue queries and ensure resolution in a timely and efficient manner. The Compliance Coordinator will also monitor for applicable regulatory compliance and research pharmacy compliance (if applicable) and communicate any deficiencies as appropriate.

14.5 Confidentiality

Information about study subjects will be kept confidential and managed according to the requirements of the Health Insurance Portability and Accountability Act (HIPAA). Those regulations require a signed subject authorization informing the subject of the following:

- What protected health information (PHI) will be collected from subjects in this study
- Who will have access to that information and why
- Who will use or disclose that information
- The rights of a research subject to revoke their authorization for use of their PHI.

In the event that a subject revokes authorization to collect or use PHI, the investigator, by regulation, retains the ability to use all information collected prior to the revocation of subject

authorization. For subjects that have revoked authorization to collect or use PHI, attempts should be made to obtain permission to collect at least vital status (e.g., that the subject is alive) at the end of their scheduled study period.

The subject binders will be maintained with in the CPDM offices, a secured floor within the Herbert Irving Pavilion and only the investigator and study staff will have access to the file.

14.6 Source Documents

Source data is all information, original records of clinical findings, observations, or other activities in a clinical trial necessary for the reconstruction and evaluation of the trial. Source data are contained in source documents. Examples of these original documents, and data records include: hospital records, clinical and office charts, laboratory notes, memoranda, participants' diaries or evaluation checklists, pharmacy dispensing records, recorded data from automated instruments, copies or transcriptions certified after verification as being accurate and complete, microfiches, photographic negatives, microfilm or magnetic media, x-rays, participant files, and records kept at the pharmacy, at the laboratories, and at medico-technical departments involved in the clinical trial.

14.7 Case Report Forms

The study case report form (CRF) is the primary data collection instrument for the study. All data requested on the CRF must be recorded. All missing data must be explained. If a space on the CRF is left blank because the procedure was not done or the question was not asked, write "N/D". If the item is not applicable to the individual case, write "N/A".

14.8 Records Retention

Records relating to a specific research activity, including research records collected by investigators, must be maintained for at least three years after completion of the research (45 CFR 46.115(b); 21 CFR 56.115(b); 21 CFR 312.62). This minimum retention period applies whether or not any participants were enrolled in the study.

If the research is FDA regulated, records should be retained for at least two years after approval of the investigational agent by FDA; if it is not approved, records should be retained at least two years after the study is terminated and FDA is notified (note the additional requirement below for clinical research studies);

Clinical records, including consent forms that document clinical intervention or clinical diagnostic procedure research-related procedures, must be retained in medical records by the institution for at least seven years, per CUMC and NYP policy which is based on state law.

15 STATISTICAL CONSIDERATIONS

15.1 Study Design/Endpoints

This is a phase II, open label, single-arm study designed to estimate the safety and efficacy of nivolumab in participants with recurrent or progressive IDH mutant gliomas who were

previously exposed to alkylating agents. The primary endpoint is to evaluate the objective response rate (partial and complete responses) to nivolumab in these participants. Secondary endpoints include determination of progression free and overall survival and duration of response. Additional exploratory endpoints include biomarker assessments including correlations of response rate with mutational load analysis, clonal evolution of tumor cell populations in IDH mutated gliomas undergoing therapy when tissue is available, and evaluation of longitudinal changes in the IDH mutant metabolite product 2-hydroxyglutamate (2HG) using magnetic resonance spectroscopy.

15.2 Size/Accrual Rate

Based on prior historical data showing an overall response rate (ORR) of 9% in recurrent high-grade gliomas (grade III and IV)³⁹, and 0% on the IDH inhibitor trial (AG-221)³ we set the null hypothesis of an ORR = 10% and the alternative hypothesis of an ORR = 30%. With one-sided $\alpha=0.05$ and $\beta=0.10$, a sample size of 33 evaluable participants will be needed to assess the preliminary efficacy of this regimen. We expect to accrue a total of 37 participants across all sites to account for a 10% of participants who may be deemed unevaluable for response.

We expect an accrual rate of 3 participants per month.

15.3 Stratification Factors

Not applicable

15.4 Analysis of Primary Endpoints

Objective Response Rates

Objective response rate is defined as the proportion of patients with a reduction in tumor size while on treatment with nivolumab. Overall objective response rate is the sum of participants with either a partial response or complete response. Tumor size as measured on MRIs every 8 weeks will be used to determine response rate. The initial MRI prior to starting on study will serve as a baseline for comparison. Partial and complete responses will be based on RANO or criteria (See **Section 13.3**). This will be used to evaluate the direct therapeutic effect of nivolumab in IDH mutant gliomas previously exposed to alkylating agents. The objective response rate will be compared to the null hypothesis using an exact test. The null hypothesis is an objective response rate of 10% based on historical data in patients with recurrent high-grade gliomas. The objective response rate and a 95% confidence interval will be reported.

A central review of all scans collected during the course of the study for all enrolled patients will be completed by the Sponsor Investigator and/or designee to review and confirm response assessment

15.5 Analysis of Secondary Endpoints

PFS and OS

PFS is defined as the time from the first dose of nivolumab to the first documented tumor progression or death due to any cause. Participants who die without a reported progression will be considered to have progressed on the date of death. Participants who did not have disease progression or die will be censored at the date of last tumor assessment. Participants who started any subsequent anti-cancer therapy without a prior reported progression will be censored at the last tumor assessment prior to initiation of the subsequent anti-cancer therapy. Participants who had surgical resection post start of study treatment will be censored at the last tumor assessment date prior to initiation of surgical resection. PFS will be determined by investigator reported response based on RANO criteria.

OS is defined as the time from the first dose of nivolumab to death due to any cause. All other participants will be censored at the last date known to be alive.

PFS and OS will be presented in Kaplan Meier curves and median with 95% confidence intervals. The duration of overall response is measured from the time measurement criteria are met for CR or PR (whichever is first recorded) until the first date that recurrent or progressive disease is objectively documented. DOR will be presented as a median with 95% confidence intervals.

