Participants treated with nivolumab will be permitted to continue nivolumab treatment beyond initial progressive disease, assessed by the investigator, as long as they meet the following criteria:

- Investigator-assessed clinical benefit
- Tolerance of study drug
- Treatment beyond progression will not delay an imminent intervention to prevent serious complications of disease progression (eg, severe symptoms due to brain mass effect)
- Participant provides written informed consent prior to receiving additional nivolumab treatment

All other elements of the main consent including description of reasonably foreseeable risks or discomforts, or other alternative treatment options will still apply.

A radiographic assessment/scan should be performed within 8 weeks of initial investigator-assessed progression to determine whether there has been a decrease in the tumor size or continued PD. The assessment of clinical benefit should be balanced by clinical judgment as to whether the participant is clinically deteriorating and unlikely to receive any benefit from continued treatment with nivolumab.

If the investigator considers that the nivolumab participant continues to achieve clinical benefit by continuing treatment, the participant should remain on the trial and continue to receive monitoring according to the time and events schedule in Section 12.2.

If at the radiographic assessment at 8 weeks of initial investigator-assessed progression the assessment determines continued PD but all the above criteria are met and the investigator considers the participant continues to achieve clinical benefit by continuing treatment, the participant may remain on the trial and continue to receive treatment and monitoring according to the time and events schedule in Section 12.2. Potential for clinical benefit should be balanced by clinical judgment as to whether the participant is clinically deteriorating and unlikely to receive benefit from continued treatment with nivolumab. A second radiographic assessment should be performed within 8 weeks of second investigator-assessed progression to determine whether there has been a decrease in the tumor size or continued PD. If this second 8-week radiographic assessment determines continued PD, then the participant should discontinue therapy and enter the follow-up period.

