 - > 25% increase in sum of the products of perpendicular diameters of enhancing lesions (over best response [smallest tumor size] or baseline if no decrease) on stable or increasing doses of corticosteroids
 - Any new enhancing measurable lesion that when added to the change in initial tumor(s) exceeds a 25% increase in cross-sectional area.
 - Clear clinical deterioration not attributable to other causes apart from the tumor (e.g. seizures, medication side effects, complications of therapy, cerebrovascular events, infection, etc.). The definition of clinical deterioration is left to the discretion of the investigator but it is recommended that a decline in the Karnofsky Performance Score (KPS) from 100 or 90 to 70 or less, a decline in KPS of at least 20 from 80 or less, or a decline in KPS from any baseline to 50 or less, for at least 7 days, be considered neurologic deterioration, unless attributable to co-morbid events or changes in corticosteroid dose.
 - Failure to return for evaluation due to death or deteriorating condition
 - Classification of progressive disease may be deferred for up to three months for patients with initial radiographic findings consistent with progressive disease (criteria a and b above) as detailed below. However, if follow-up imaging after three months confirms progression or if the patient experiences significant clinical decline at any time, the date of actual progression will be back-dated to the first date that the patient met criteria for progression and such patients should discontinue further immunotherapy.

- **Stable disease (SD).** All of the following criteria must be met:
 - Does not qualify for CR, PR, or progression.
 - All measurable and non-measurable sites must be assessed using the same techniques as baseline.
 - Stable clinically.
- **Unknown response status.** Progressive disease has not been documented and one or more measurable or non-measurable lesions have not been assessed.

Table 13.1 RANO Response Criteria Summary

	CR	PR	SD	PD#
T1 + Gd	None	≥50% decrease	<50% decrease to <25% increase	≥25% increase (including new lesions)*
T2/FLAIR	Stable/Decrease	Stable/Decrease	N/A	N/A
New Lesion	None	None	None	Present (contributing to lesion size)*
Corticosteroids	None	Stable/Decreased	Stable/Decreased	Stable/Increasing
Clinical Status	Stable or Improved	Stable or Improved	Stable or Improved	Clinical decline*
Requirement for Response	All	All	All	Any*

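### The PFS resection-censoring sentence in Section 15.5 lacks the no-prior-progression limit of the sentence before it; applied as written, it censors progressions already documented before surgery

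*Combined protocol and SAP*

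**What the plan says.** Section 15.5 defines PFS as "the time from the first dose of nivolumab to the first documented tumor progression or death due to any cause". Four coding sentences follow:

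- Death: "Participants who die without a reported progression will be considered to have progressed on the date of death".
- General censoring: "Participants who did not have disease progression or die will be censored at the date of last tumor assessment".
- New therapy: "Participants who started any subsequent anti-cancer therapy without a prior reported progression will be censored", at the last tumor assessment before that therapy.
- Resection: "Participants who had surgical resection post start of study treatment will be censored at the last tumor assessment date prior to initiation of surgical resection".

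The same section runs duration of response "until the first date that recurrent or progressive disease is objectively documented" and bases PFS on investigator-reported RANO response.

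Section 13.6 also defines PFS, as time to progression or death, and gives no PFS censoring rules. That is silence, not a conflict. No section restores the limit to the resection sentence or ranks the coding sentences.

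Surgery after the start of treatment is foreseen. Sections 5.5 and 15.6 plan to study tissue from operations for recurrence after nivolumab. Section 11.2 covers surgery for presumed progression and treats a participant whose pathology shows pseudoprogression as not having progressed.

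**The concern.** Two adjacent sentences handle similar situations, and only one excludes participants who have already progressed. An analyst who programs the resection sentence literally will take a documented progression and record it as censored because an operation followed. That conflicts with the PFS definition in the same section. For a responder, it also lets one progression scan end duration of response without counting as a PFS event.

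Surgery in this disease is often prompted by progression, so the censoring would be related to outcome. Two analysts working from the same data and the same text could report different PFS curves and medians. Section 3 hypothesises a better median PFS than historical controls, and the literal reading tends to move PFS in that direction.

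**Working it through.** The plan states no PFS figure to reproduce. The check sets the rules side by side and then sizes the literal reading under stated assumptions.

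**1. Coding of three cases**

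| Case | PFS definition and death sentence | Resection sentence as written |
|---|---|---|
| RANO progression on a scan, then resection | Event at progression | Censored at last scan before surgery |
| Resection with no reported progression, then death | Event at death | Censored at last scan before surgery |
| New therapy with no reported progression, then death | Event at death | Not applicable, but the new-therapy sentence also censors |

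The first row is the defect. The second and third rows show a separate gap, a missing precedence rule, which both censoring sentences share.

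**2. Direction**

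The last scan before surgery is either the progression scan or a later one; Section 11.2 says "Participants treated with nivolumab will be permitted to continue nivolumab treatment beyond initial progressive disease", so later scans can exist. In both cases an event is removed and follow-up is not shortened, so the curve stays level or rises.

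The exception is clinical progression between scans, which Section 13.3 allows. Suppose the last scan is at week 16 and clinical progression at week 20. The literal rule censors at week 16. The event is lost, but the participant also leaves the risk set four weeks early, so an event in someone else at week 18 makes a larger drop. The curve need not be higher at every time point.

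**3. Inputs for size**

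- n = 37 (Sections 5.7 and 15.2) and scans every 8 weeks (Section 12.2).
- Median PFS of 13.9 weeks, from the PD-L1 inhibitor study in Section 3, which is a different cohort; or 26 weeks (assumed).
- Exponential PFS, and no other censoring before week 24 (assumed).
- f, the share of progressions followed by resection: not in the documents, so assumed.

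**4. Baseline**

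The probability of progression per 8-week interval is q = 1 − exp(−ln 2 × 8/m).

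- m = 13.9: q = 0.329; S(8), S(16), S(24) = 0.671, 0.450, 0.302.
- m = 26: q = 0.192; S(8), S(16), S(24) = 0.808, 0.653, 0.527.

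**5. One progression recorded as censored**

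Take one progression at scan k, with surgery before the next scan. About 37 × S(8k) participants remain after that scan, so S(24) rises by S(24)/(37 × S(8k)).

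| Progression at week | m = 13.9 | m = 26 |
|---|---|---|
| 8 | 0.302/(37 × 0.671) = 1.2 points | 0.527/(37 × 0.808) = 1.8 points |
| 16 | 0.302/(37 × 0.450) = 1.8 points | 0.527/(37 × 0.653) = 2.2 points |
| 24 | 1/37 = 2.7 points | 1/37 = 2.7 points |

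Weighting by the expected share of progressions at each scan gives 1.7 and 2.2 points. A simulation of 10,000 trials gave 1.75 and 2.18.

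**6. A share f of progressions recorded as censored**

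With surgery right after the progression scan, S(24) = (1 − (1 − f)q)³.

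- m = 13.9, f = 10%: (1 − 0.9 × 0.329)³ = 0.349, against 0.302.
- m = 26, f = 10%: (1 − 0.9 × 0.192)³ = 0.566, against 0.527.

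**7. Sampling error for comparison**

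1.96 × √(0.302 × 0.698/37) = 0.148, and 1.96 × √(0.527 × 0.473/37) = 0.161. The 95% interval is therefore roughly ±15 points.

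**The case against.** The strongest reply is that the sentence is loosely worded and no sensible analyst would apply it literally. The PFS definition ends at the first documented progression, and general censoring is for those who neither progressed nor died. Section 13.3 says that for deferred progression "the date of actual progression will be back-dated to the first date that the patient met criteria for progression". Section 12.3 requires no further tumor assessments after on-study progression. Read literally, an operation at any later date would erase a progression, which is an unlikely intention. This stands as far as it goes: the narrower reading is plausible and may be what was meant. It is not stated, though, and the limit's presence in one sentence and absence from the next invites the opposite inference.

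The objection to the numbers also stands. The documents give no resection rate, the 13.9-week median comes from a study with 4 known IDH1-mutant participants among 31, and the exponential form is an assumption.

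A reader might infer more than the documents support:

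- *That reported PFS will be inflated.* This follows only from the literal reading, and not at every time point when progression was clinical and between scans.
- *That the clash with the death sentence is peculiar to resection.* The new-therapy sentence, limit included, has the same clash.
- *That progression shown only by pathology at surgery is wrongly lost.* Section 15.5 bases PFS on RANO, while the pathology text in Section 13.3 sits in the iRANO guidance. Whether such a finding is a PFS event is the sponsor's decision.
- *That censoring after surgery showing pseudoprogression also biases PFS upward.* It discards follow-up, including progression-free time; no upward bias is shown.

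**Conclusion.** The point holds as an error in a stated rule. As written, the resection sentence gives the wrong result for a participant with documented progression before surgery, and nothing else in the protocol corrects it. The omission is certain; whether it would alter the reported curve depends on how the analyst reads the sentence and how many participants are resected.

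Under the literal reading, with n = 37 and exponential PFS at a median of 13.9 or 26 weeks, each early progression recorded as censored adds about 2 points to 24-week PFS. An assumed 10% of progressions resected would move it from about 30% to 35%, or from about 53% to 57%. These shifts are well inside the sampling error, but they are systematic and avoidable.

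A reader might infer that the trial's main conclusion is at risk. It is not: PFS is secondary and descriptive, with no test or threshold, and ORR, OS and the sample size do not depend on this sentence.

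**What to change.** In Section 15.5:

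1. Limit the resection sentence in the same way as the new-therapy sentence: a participant resected after starting treatment, with no progression reported before the operation, is censored at the last tumor assessment before it.
2. State that RANO progression documented before resection is an event at the first date the criteria were met, except where Section 11.2 deems the participant not to have progressed because pathology shows pseudoprogression.
3. State one precedence rule between the death sentence and both censoring sentences, so that deaths after resection and deaths after new therapy are coded alike.
4. Add one sensitivity analysis of PFS with no censoring at resection.

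These rules should be fixed before PFS is analysed. The cost is a few sentences and minor analysis work; Section 6.9 already keeps participants who stop treatment on study for progression and death. PFS may look slightly less favourable than under the literal rule. Treatment and surgical decisions are not affected.
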